17.4 Partial or Missing Transfusion Dates

For transfusion summaries, the missing day of transfusion start date will conservatively be set to:

- First day of the month that the transfusion occurred if this is after the date of the start of first treatment.
- One day after the first treatment if this is the same month that the transfusion occurred.
- The 15th of the month and year if the transfusion month and year are before the month and year of the first treatment.

If the onset date of the transfusion is missing both day and month, it will be set to:

- January 1 of the year of onset, as long as this is after the first study treatment.
- One day after the first study treatment if this is the same year that the transfusion occurred.
- July 1st of the year if the transfusion year is before the year of the first study treatment.

If the day of resolution of transfusion is missing, it will conservatively be set to the last day of the month or 30 days after the last dose of study treatment if this day is in the same month and year, whichever is earlier. If the day of resolution of transfusion is missing both day and month, it will conservatively be set to the last day of the year or 30 days after the last dose of study treatment if this day is in the same year, whichever is earlier.

All missing and partial dates will be presented “as is” in listings.

17.5 Partial or Missing Concomitant Medication and Supplemental Procedure Dates

For concomitant medication, when missing the start date information the following imputation will be applied:

Derive data only with the missing day of the month:

- First day of the month that the CM occurred if this is after the date of the start of first treatment.
- One day after the first treatment if this is the same month that the CM occurred.
- The 15th of the month and year if the CM month and year are before the month and year of the first treatment.

Derive data if both day and month are missing:

- January 1 of the year of onset, as long as this is after the first study treatment.
- One day after the first study treatment if this is the same year that the AE occurred.
- July 15th of the year if the CM year is before the year of the first study treatment.

When missing the end date information the following imputation will be applied:

Derive data only with the missing day of the month:

- Set as the last day of the month

Derive data with both missing day and month:

- set as December 31th

All missing and partial dates will be presented “as is” in listings

12.1 Analysis Windows

Analysis windows will be defined as follows:

Endpoint	Nominal Visit	Nominal Study Day	Analysis Windows (in days)
Spleen volume (SPV)	Week 12	84	(63 to 105)
	Week 24	168	(147 to 189)
	Week 36	+3 months pos-24 week	+/- 21 days
	...		
Total Symptom Score (TSS)	Week 12	84	(63 to 105)
	Week 24	168	(147 to 189)
	Week 36	+3 months pos-24 week	+/- 21 days
	...		
Patient Global Impression Assessment (PGIC)	Week 12	84	(63 to 105)
	Week 24	168	(147 to 189)
	Week 36	+3 months pos-24 week	+/- 21 days
	...		

12.2 Laboratory Results Reported as a Range

Laboratory results that are reported as less than or greater than a certain value (limit of quantification) or as a range of values will be imputed for analysis using the rules described below.

Myeloblast Percentages

- Myeloblast results in the hematology data reported as $<X\%$ will be imputed with the value $(X-1)\%$ for analysis.
- Myeloblast results in the hematology data reported as $\leq X\%$ will be imputed with the value $X\%$ for analysis.
- Myeloblast results in the hematology data reported as $X-Y\%$ will be imputed with the value $Y\%$ for analysis.

Other Laboratory Results

- Laboratory results reported as $<X$ will be imputed with the value $(X-1)$ for analysis. Results reported as $<X.Y$ will be imputed by subtracting one from the last significant digit (Y). Results reported as <0.1 will be imputed as 0 for analysis as long as the normal range extends to 0.
- Laboratory results reported as $>X$ will be imputed with the value $(X+1)$ for analysis. Results reported as $>X.Y$ will be imputed by adding one to the last significant digit (Y).

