8.2 BASELINE DISEASE CHARACTERISTIC VARIABLES

Spleen length by physical exam, baseline platelet count and category (\leq 50,000/ μ L vs. $>$ 50,000/ μ L to \leq 100,000/ μ L vs. $>$ 100,000/ μ L), baseline hemoglobin and category (< 100 g/L vs. \geq 100 g/L), peripheral blasts percentage and category (< 1% vs. \geq 1%), white blood cell count and category (\leq 25x10 9 /L vs. $>$ 25x10 9 /L), current MF diagnosis (PMF vs. PPV MF vs. PET MF), time since current MF diagnosis, gene mutation status (JAK2V617F vs. other JAK2 vs. MPL vs. CALR vs. Triple Negative vs. Other vs. None), abnormal cytogenetics (Yes vs. No), unfavorable karyotype (Yes vs. No), current DIPSS score (1 vs. 2 vs. 3 vs. 4 vs. 5 vs. 6), DIPSS plus score (1 vs. 2 vs. 3 vs. 4 vs. 5 vs. 6), transfusion history (within 90 days prior to (Informed Consent date through the treatment start date + 1)), red blood cell (RBC) transfusion dependence as defined by the Gale criteria (Gale et al. 2011; Table 1), and platelet transfusion dependence (Table 2).

Table 1 – Definitions of Red Blood Cell Transfusion Dependence and Independence

	RBC Transfusions
RBC transfusion dependence	\geq 2 units/month
RBC transfusion independence	None
Reduced RBC transfusion dependence	50% decrease
Gale et al. 2011	

Table 2 – Definitions of Platelet Transfusion Dependence and Independence

	Platelet Transfusions
Platelet transfusion dependence	Any episode of platelet transfusion during the past month
Platelet transfusion independence	No platelet transfusion during the past month

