11.2.1 HEMATOLOGY

Hematology parameters including CBC, differential, platelet count and hemoglobin A1C among others will be evaluated at screening, baseline, the end of week 4, the end of Week 12, the end of Week 24 or the end of treatment visit, every 3 months during the follow-up period, and 30 days after the last dose of study treatment.

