13.2 CLINICAL LABORATORY MEASUREMENTS

The counts and percentages of the shifts in CTCAE grade from baseline to the worst and last post-baseline grade (not including the 30 post treatment end visit in the evaluation of worst grade at post-baseline) will be presented for each laboratory measure. Descriptive statistics of change and percent change from baseline in laboratory values will be presented by visit. Plots of the shift from baseline to worst post-baseline in selected parameters by treatment arm will be presented. In the case of hemoglobin, a parameter that is hugely affected by transfusions, the percent change over time will be explored in patients who did not have a transfusion in the 90 days prior to informed consent or on study.

Laboratory results (including serum pregnancy) will be provided in a subject list and include at minimum subject id, age, treatment arm, visit, assessment date, laboratory category, laboratory parameter, results and lab units.

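### SAP 12.2 turns a blast result of <1% into 0, so the percent-change table of SAP 13.2 loses rises from below the limit and counts every fall to below it as -100%

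*SAP*

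**What the plan says.** The imputation rules are in the SAP section headed Laboratory Results Reported as a Range (numbered 12.2, near the end). For blasts: "Myeloblast results in the hematology data reported as $<X\%$ will be imputed with the value $(X-1)\%$ for analysis". A blast report of ≤X% takes the value X%, and a report of X-Y% takes the upper end, Y%. For other analytes, <X becomes X-1. Decimal results below a limit follow a last-digit rule ("will be imputed by subtracting one from the last significant digit (Y"), with one special case: a result of <0.1 "will be imputed as 0 for analysis as long as the normal range extends to 0".

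SAP 13.2 uses the imputed values: "Descriptive statistics of change and percent change from baseline in laboratory values will be presented by visit". It exempts no analyte. SAP 11.2.1 puts the white-cell differential in scope ("Hematology parameters including CBC, differential, platelet count and hemoglobin A1C among others"), and SAP 12.2 itself treats myeloblasts as part of the hematology data.

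SAP 17.1 defines the safety baseline as the last assessment before treatment starts. Nothing in the SAP says what to do when that baseline is 0. SAP 8.2 also tabulates "peripheral blasts percentage and category", cut at <1% versus ≥1%.

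**The concern.** Percent change divides by the baseline value. If a baseline of <1% is analysed as 0, the patient has no percent change, whether blasts later stay below 1% or rise to 6%. A patient who moves the other way, from 6% to <1%, does have a percent change, and it is set at the largest possible fall. The table therefore keeps one direction of movement across the limit and discards the other.

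Low blast counts are expected here, because inclusion criterion 8 (Protocol 4.1.1) requires peripheral blasts below 10%. A reader comparing doses on the by-visit blast table could see an apparent fall in an arm whose blasts have not moved.

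A smaller problem concerns the baseline blast category. Reports of ≤1% and 0-1% are both imputed as 1% and so counted as ≥1%, although either is compatible with a count below 1%.

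**Working it through.** The plan states no figure for this point, so there is nothing to reproduce. The check applies the SAP rules to percent change = 100 × (later - baseline) / baseline.

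**1. Single patients, blast limit <1% (imputed 0).**
- Baseline <1%, later <1%, 2% or 5%: division by zero, no value.
- Baseline 2%, later <1%: 100 × (0 - 2)/2 = -100%. The reports show only a fall of more than 50%.
- Baseline 5%, later <1%: -100%. The reports show only a fall of more than 80%.
- Baseline 6%, later <1%: -100%. The reports show only a fall of more than 100 × (6 - 1)/6 = 83%.

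**2. Where zeros arise.** A limit of <1 gives 0, and <0.1 gives 0 where the normal range reaches 0. Other limits behave differently:
- <0.2 becomes 0.1. Baseline <0.2 rising to 0.4 scores 100 × (0.4 - 0.1)/0.1 = +300%, when the rise is known only to exceed 100 × (0.4 - 0.2)/0.2 = +100%.
- <5 becomes 4. Baseline <5 rising to 10 scores +150%, when the rise is known only to exceed +100%.

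At such limits nobody is lost, and rises can be exaggerated.

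**3. One arm (all inputs assumed).** Take 50 patients, the protocol's maximum per arm: 25 at <1% and 25 at 6%. Ten rise from <1% to 6%, ten fall from 6% to <1%, and 30 do not move.
- Mean absolute change = (10 × 6 - 10 × 6)/50 = 0 points, n = 50.
- Mean percent change = (10 × -100% + 15 × 0%)/25 = -40%, n = 25. The median is 0%.
- With five moving each way: (5 × -100% + 20 × 0%)/25 = -20%.

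**4. Simulation with no true change (all inputs assumed).** There were 400,000 patients per scenario. Blasts were lognormal with between-patient log-SD 1.0, and values below 1% were reported as <1%. The fourth and fifth columns are median percent changes in the patients left after exclusion.

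| Median blasts | Within-patient log-SD | Excluded | SAP rule | Same patients, true values | Share with a fall, SAP rule |
|---|---|---|---|---|---|
| 0.5% | 0.3 | 75% | -11.1% | -10.4% | 60% |
| 0.5% | 0.6 | 72% | -38.7% | -31.2% | 68% |
| 1% | 0.3 | 50% | -7.0% | -6.8% | 57% |
| 1% | 0.6 | 50% | -23.8% | -21.8% | 62% |
| 2% | 0.3 | 25% | -3.6% | -3.6% | 53% |
| 2% | 0.6 | 28% | -13.4% | -13.1% | 57% |
| 4% | 0.3 | 9% | -1.6% | -1.6% | 52% |
| 4% | 0.6 | 12% | -6.3% | -6.2% | 53% |

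Over all patients the true median lies between -0.2% and 0.2%, and mean absolute change under the SAP rule is 0.00 to 0.01 points. Most of the shift in the median comes from excluding patients with a zero baseline (selection followed by regression to the mean). Scoring -100% acts mainly on the mean, which it lowers by 1.7 points (7.6 to 5.9) to 14.4 points (-4.9 to -19.3) in the same patients.

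**5. Baseline category.** <1% becomes 0 and is correctly filed as <1%. ≤1% becomes 1% and 0-1% becomes 1%; both are filed as ≥1%, which neither report shows.

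**The case against.** The strongest reply is that the harm is small and partly visible. SAP 6.1 requires n, quartiles and the median, so in the illustration the reader would see n = 25 beside n = 50 and a median of 0%. Absolute change is already planned and stays defined; for a blast result of <1% the imputation moves it by at most 1 percentage point. A true 0% count also has no percent change, so the missing zero-baseline rule matters as much as the imputation. The documents do not say how often these strings occur. All of this stands. It limits the size of the problem but does not supply the missing rule, and the simulation shows that the median need not stay at 0.

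Four stronger readings are tempting, and the documents do not support them:
- **All laboratory percent-change tables are biased towards falls.** Step 2 shows otherwise for limits such as <0.2, <2 or <5.
- **Leukemic transformation would be hidden.** Protocol 3.2 defines it by absolute blast thresholds of 20%, and SAP 13.3.6 lists it by patient with status, date and form.
- **The baseline blast category is overstated in general.** Only ≤1% and 0-1% strings are affected, with unknown frequency. The category is a descriptor; it is neither a stratification factor nor a named subgroup.
- **Changes in how a limit is printed create false falls.** A blast sequence of <5% then <1% would indeed be analysed as 4% to 0%. But scheduled and unscheduled samples go to a central laboratory (Protocol 9.2), and nothing shows that one analyte would be reported in two formats.

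**Conclusion.** The point holds, as a minor one. Followed as written, SAP 12.2 and 13.2 give a percent-change summary that omits rises from below the limit and is tilted towards falls. This applies to myeloblasts and to any other analyte whose baseline is 0 or imputed as 0.

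The size cannot be determined from the documents. On assumed inputs, the illustrated arm mean is -20% to -40% with no net change, and the simulated median is -1.6% to -38.7% with no true change. The direction follows from the rules; the magnitudes rest wholly on the assumptions.

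A reader might infer that dose selection is compromised. It is not: spleen volume, TSS and the primary safety measure (SAP 13) do not use these values. There is no hypothesis test, the same rule applies in every arm, and no distortion between doses has been shown. The filing of ≤1% and 0-1% as ≥1% is a separate, smaller misclassification.

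**What to change.** In SAP 13.2, do not present percent change for myeloblasts or for any analyte with baselines that are 0 or imputed as 0. For these:
- present absolute change from baseline by visit;
- for blasts, add a by-arm shift table with cut-points already in the documents: <1%, 1 to <10%, 10 to <20%, ≥20% (SAP 8.2, Protocol 4.1.1, and Protocol 3.2 with SAP 13.3.6);
- report the number of censored values by arm and visit;
- show a result as not determinable, both in the SAP 8.2 baseline category and in the shift table, when its reported range straddles a cut-point.

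In the illustrated arm the shift table would show ten patients moving up, ten moving down and 30 unchanged.

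Percent change can stay for other analytes. Replacing <X by X/2 is optional. It gave a median of 0.0 in every simulated scenario, but it leaves true zeros without a percent change and would still turn <5% followed by <1% into a fall from 2.5% to 0.5%.

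The cost is SAP wording, minor reprogramming, and the loss of the percent-change column for what should be a few analytes.
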